At the time of collection, samples will be kept on ice or refrigerated (with the exception of stool which will be kept in a freezer) in the pediatric clinical research unit or in [name] laboratory (Rm 4015 of ACRI) until they can be transported to the research or hospital laboratory.

For testing to be completed by the Arkansas Children's hospital laboratory (e.g., HbA1c), sample(s) will be labeled with the participant's medical label generated through EPIC which includes the participant's name, date of birth, gender, and medical record number. This sample will be provided to the hospital laboratory where they will complete the testing, storage, and disposal of the sample per their standard operating procedures. Results will be reported through the participant's medical record.

For testing to be completed by [name] laboratory, samples will be kept at -80°C once the initial processing and analyses have taken place. These samples will be stored in the Arkansas Children's Research Institute, Room R4017 Freezers 4017FT12 or R4017FT8 or R2108 Freezer R2108FT16. Cryopreserved samples may also be kept under liquid nitrogen in the Arkansas Children's Research Institute, Room R4017. These are monitored continuously for proper temperature and working condition. None of a subject's personal identifiers will be present on any biological sample, except the unique subject ID, study visit number, and the study acronym. The samples may be used until they are used up for research on pediatric nutrition or metabolism.

At any time if the subject decides that he/she does not want to participate anymore, that subject's data will be included as part of the planned analysis of study data. No more information will be collected after withdrawal, however all data and samples collected prior to withdrawal will still be used.

Information pertaining to this study will be made publically available through the ClinicalTrials.gov website.

Data Analysis

Title: Immunometabolism in Pediatric Obesity

PI: [name].

Prior to any analyses, endpoints data for each group will be closely inspected for the potential presence of unusual values; effort will be made to conserve all data. Analyses will be carried out in SAS 9.4 (SAS Institute, Cary NC) at the 5% significance level; point and 95% interval estimates will be obtained for relevant metabolic group comparisons. Parametric techniques will be first choice and nonparametric equivalents if assumptions are not met. Special attention will be paid to unequal variances.

The study planned four groups of children: lean, healthy obese/overweight, insulin-resistant obese/overweight, and overweight/obese with T2D. Primary comparison of interest are these three: the average of insulin-resistant and T2D obese children compared to (i) lean children and (ii) healthy obese children; and (iii) lean children compared to healthy obese children. Outcomes important to this aim are proportions of T_{reg} cells among circulating CD4 $^{+}$ T cells and CD4 $^{+}$ T glycoATP and mitoATP production. Initially, we will use a one-factor ANOVA to analyze these outcomes (possibly with suitable transformations). Comparisons of interest will then be made with 0.05 significance level *t*-tests conducted within the ANOVA framework.

The requested sample sizes will provide about 0.80 power for detecting differences in means of size 0.8 SD for comparisons (i) and (ii) and size 0.9 SD for comparison (iii), where SD is the within-group standard deviation (a.k.a., root mean square error from the ANOVA). For proportions of T_{reg} cells – a primary outcome of interest, an estimate of the SD is 2.3 percentage points (ref Table 1 of Arismendi et al.⁴²). So, if the means differ by at least 1.85 percentage points in comparisons (i) & (ii) and by 2.10 percentage points for comparison (iii), we will be able to detect these differences with a reasonably high probability (0.80 or higher).

Ethical Considerations

This study will be conducted in accordance with all applicable government regulations and University of Arkansas for Medical Sciences research policies and procedures. This protocol and any amendments will be submitted and approved by the UAMS Institutional Review Board (IRB) to conduct the study.

The formal consent of each subject, using the IRB-approved consent form, will be obtained before that subject is submitted to any study procedure. All participants for this study will be provided a consent form describing this study and providing sufficient information in language suitable for participants/parent/legally authorized guardian to make an informed decision about their participation in this study. The person obtaining consent will thoroughly explain each element of the document and outline the risks and benefits, alternate treatment(s), and requirements of the study. The consent process will take place in a quiet and private room, and participants/parent/legally authorized guardian may take as much time as needed to make a decision about their participation. Participation privacy will be maintained and questions regarding participation will be answered. No coercion or undue influence will be used in the consent process. This consent form will be signed by the parent or legally authorized guardian. Written assent will be obtained from participants aged 7-17 years, inclusive. A copy of the

Title: Immunometabolism in Pediatric Obesity

PI: [name].

signed consent will be given to the participants/parent/legally authorized guardian, and the informed consent process will be documented in each subject's research record. A signed copy of the consent form may be placed in patients' medical record. We request a waiver of consent for subjects who turn 18 while their samples are still available for use and who may still have data collected from their medical records, for the purposes of this study and/or for future research studies if consent obtained for this purpose. If the waiver is approved by the institutional review board and samples are still available for use/data is still being collected when a participant turns the age of 18, the participant will not be re-contacted to sign a consent form. However, these participants can contact study staff after they turn 18 to ask that any remaining samples be removed and data collection stop. In addition, participants may be re-contacted about participating in future research studies.

Initially, samples will be stored at Arkansas Children's Hospital and/or Arkansas Children's Research Institute. The sample provided to the Arkansas Children's Hospital laboratory will be tested, stored, and disposed of per their standard operating procedures and will not be used for future research studies. The information collected at the study visit, urine, and stool samples, and remaining blood samples may be stored indefinitely and may be used for future research studies on pediatric nutrition or metabolism. Prior to the information collected at the study visit and samples being used for future research studies, the PI will assess the ethics and scientific merit of the proposed research with the samples, and proposed future research will be reviewed by the IRB as may be required. The samples and health information collected for the study visit may be shared with researchers at the University of Arkansas for Medical Sciences, Arkansas Children's Hospital, or Arkansas Children's Research Institute. The samples may be shared with an outside group. The samples will only have a study ID number, study visit number, and study acronym to maintain confidentiality. If participants decide they no longer want us to use their samples for future research studies, they may ask the study staff that the sample be removed. If the sample has been shared or if publication of results has occurred, then we may not be able to remove the sample.

A summary of the study visit will be provided to the parent indicating the participant's anthropometric and body composition measurements and the CES-DC results from the study visit. The parent will be directed to follow-up with their child's PCP if they have concerns. If the parent has concerns and the child does not have a PCP, research staff will assist the parent with identifying a PCP. If participant scores a 15 or greater on the CES-DC, suggesting that the participant expresses symptoms of depression, research staff will follow-up with the parent to explain these results, discuss the need to follow-up with the child's PCP, and provide the parent with the 'Resources to Seek Help for Depression in Children' form. If the child does not have a PCP, research staff will assist the parent with identifying a PCP.

Dissemination of Data

Results of this study may be used for presentations, posters, or publications. The publications will not contain any identifiable information that could be linked to a participant.

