Obesity is strongly linked to systemic inflammation with increased circulating pro-inflammatory cytokines and adipokines and elevated C-reactive protein (CRP) reported in obese children as young as age three¹⁰⁻¹⁵. Examining NHANES data from over sixteen thousand children, Skinner et al¹⁵ found that prevalence of C-reactive protein (CRP) levels >1mg/L was greater in very obese children beginning at age 3 and continued through adolescence, with greater than 80% of very obese adolescents having CRP >1mg/L as compared to 18% of lean adolescents. While the dataset did not permit controlling for pubertal age, similar results were found even when very narrow age groups were compared. In a smaller study of children ages 7-14 years, Codoner-Franch et al¹⁶ classified obese children as metabolically healthy or at risk based on well-defined criteria, and they reported CRP, Tumor necrosis factor α (TNF α) and Interleukin (IL) 6 were all increased in obese children with or without metabolic risk factors, suggesting that inflammation may appear early in obesity before metabolic alterations. Inflammation is considered pivotal to the development of obesity-related metabolic disorders including insulin resistance, T2D¹⁷⁻¹⁹ and cardiovascular dysfunction^{20, 21}. Modulation of inflammation in obese children provides a putative “target” for therapeutic intervention.

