Suppression of inflammation is a function of regulatory T cells (T_{regs}), a subset of CD4 $^{+}$ T cells also responsible for maintenance of peripheral tolerance and suppression of antigen-specific immune responses. However, decreased circulating T_{regs} have been reported in T2D²² and obese^{23, 24} adults. Wagner et al²⁴ found that reduced T_{regs} predicted a CRP level greater than 3mg/L and may therefore predict those at increased cardiovascular risk; however, a separate group reported no differences in T_{regs} between severely obese subjects with and without hypertension²³. As in humans, T_{regs} are reduced in several mouse models of obesity, especially VAT-resident T_{regs} , with a concomitant increase in VAT-resident T effector cells^{25, 26}. A critical role for T_{regs} in the development of insulin resistance has been demonstrated in these models. Winer et al²⁵ elegantly demonstrated that adoptive transfer of CD4 $^{+}$ T cells into lymphocyte deficient DIO Rag1 $^{-/-}$ mice reduced weight gain and improved glucose tolerance. *In situ* induction of T_{regs} in HFD obese wild-type mice with anti-CD3 antibody also resulted in improved glucose tolerance and insulin sensitivity, which persisted for months despite being maintained on

HFD. Feuerer et al²⁶ demonstrated that depletion of adipose T_{regs} in transgenic mice expressing the diphtheria toxin receptor in T_{regs} induces insulin resistance and increased inflammatory mediators in the adipose tissue. Conversely, *in situ* induction of T_{regs} with recombinant IL-2 and IL-2 monoclonal antibody increased VAT-resident T_{regs} and improved glucose tolerance in HFD obese mice. Findings from these two landmark studies have been replicated in other mouse models of obesity^{27, 28}. Targeting T_{regs} may modulate inflammation in obesity; however, whether T_{regs} are altered in early stages in obesity (e.g. overweight/obese children) remains unknown. In this study, we will fill an important research gap by testing whether obese children exhibit decreased circulating T_{regs} as compared to healthy lean children.

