Figure 2: The ATP production rate assay demonstrates increased % glycolysis-derived ATP production in PBMC from T2D children. Oxygen consumption rate (OCR) (A) and Proton Efflux Rate (PER) (B) are plotted over time in PBMCs from lean, obese (OB) and type 2 diabetic (T2D) children. Injections of Oligomycin (oligo) and Antimycin A (AMA) and Rotenone (ROT) are indicated. (C) Glycolytic ATP production rate (glycoATP) and mitochondrial ATP production rate (mitoATP) are calculated from OCR and PER. (D) % glycolysis and % OXPHOS-derived ATP production are calculated. * $p=0.032$

Methods: Freshly isolated PBMC from lean ($n=8$), obese (OB; $n=11$), and treatment-naive type 2 diabetic (T2D; $n=2$) children were plated at 2.5×10^6 cells/well in RPMI 1640 with 1mM HEPES, 2mM glutamine, 1mM pyruvate and 11mM glucose on poly-D-lysine coated XF96 plates. Plates were centrifuged at 100xg with no brake to adhere cells to well bottoms. After a 30 min incubation in a 37°C non-CO₂ incubator, cells were assayed in a Seahorse XF96.

note regarding this data: 1) these data are from PBMC, a mixed population of cells including monocytes and lymphocytes of various subtypes rather than purified CD4⁺ T cells as proposed in this study; 2) the obese subjects have not been classified as metabolically healthy or unhealthy; 3) the age of the T2D subjects is greater (16.5±0.1 years; mean±SD) than the other groups (lean: 6.8±1.1 years; obese: 7.9±1.4 years). In the studies proposed herein, we will match groups on age and subgroup obese subjects as metabolically healthy and unhealthy based on insulin sensitivity. Further, after measuring high sensitivity CRP (hsCRP), we will compare subjects with hsCRP values in the top quartile to the other groups to determine whether the % glycolysis is higher in CD4⁺T cells from those obese subjects with inflammation.

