OXPHOS/Glycolysis (OCR/ECAR; **Figure 3C**). These data demonstrate our ability to measure mTOR activation in small numbers of immune cells from children.

Hypothesis, Specific Aims, and Objectives

In this study, we hypothesize that compared to lean children, circulating CD4⁺T cells from obese children with elevated biomarkers of inflammation will have fewer T_{regs} and will exhibit increased mTOR-driven glycolysis. Metformin treatment will increase T_{regs} and shift the metabolic phenotypes of CD4⁺T cells towards AMPK-driven OXPHOS. We will test these hypotheses by executing the following Specific Aim:

Specific Aim 1. Compare the immune and metabolic phenotypes of circulating CD4⁺T cells between lean children and overweight/obese children.

Hypothesis: circulating CD4⁺T cells from obese children with elevated biomarkers of inflammation will have fewer T_{regs} and will exhibit increased mTOR activation and % glycolysis-derived ATP production as compared to CD4⁺T cells from lean children.

Specific Aim 2. Compare the immune and metabolic phenotypes of circulating CD4⁺T cells between T2D children before and after metformin.

Hypothesis: In obese T2D patients, metformin treatment will increase circulating T_{regs}, as well as AMPK activation and % OXPHOS-derived ATP production in CD4⁺ T cells.

Study Design and Procedures

This study consists of:

1. An observational cross sectional immune and metabolic analysis of several groups of children including lean, overweight/obese, and T2D.
2. A prospective immune and metabolic analysis of newly diagnosed children with T2D or insulin resistance who will be or were recently prescribed metformin as part of their clinical care.

Children with T2D or insulin resistance who will be or were recently prescribed metformin, will be asked to complete two study visits. If completed, the second visit will occur 6 months (+/- 2 weeks) after beginning metformin as part of their clinical care. All other children, will be asked to complete only the first visit.

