to complete the procedure(s). At the first, second, or reattempt visits, participants/parents may be given up to \$20 in ACRI merchandise and/or child-friendly stickers. Food and drinks may be provided during study visits following the fasting blood draw.

Study Population

110 children ages 5-17 years old will be recruited with the goal that approximately 80 subjects stratified across the following groups will complete the study: i) healthy lean (approximately n=20); ii) overweight/obese (approximately n=40, with the anticipation that approximately 20 of these children will be insulin resistant); iii) overweight/obese with T2D and prescribed Metformin (approximately n=20). Every attempt will be made to ensure that the desired number for each group is achieved and groups are balanced with respect to age, sex and ethnicity.

Inclusion Criteria:

- Age 5-17 years, inclusive
- Either healthy lean ($BMI \geq 5^{\text{th}}$ percentile and $< 85^{\text{th}}$ percentile for age/sex) or overweight ($BMI \geq 85^{\text{th}}$ percentile and $< 95^{\text{th}}$) or obese ($BMI \geq 95^{\text{th}}$ percentile for age/sex)
- For those with $BMI \geq 85^{\text{th}}$ percentile for age/sex, parental verbal confirmation that the child had a history of $BMI \geq 85^{\text{th}}$ percentile for age/sex for at least six months prior to study enrollment

OR

- Age 5 years - 17 years 5 months, inclusive
- Either overweight or obese ($BMI \geq 85^{\text{th}}$ percentile for age/sex)
- Parental verbal confirmation that the child had a history of $BMI \geq 85^{\text{th}}$ percentile for age/sex for at least six months prior to study enrollment
- Diagnosed with type 2 diabetes mellitus or insulin resistance
- Prescribed metformin (either not yet taking or began taking within 3 weeks of enrollment)

Exclusion criteria:

- Having an infection (viral, respiratory, gastrointestinal) in the previous 4 weeks
- Genetic or physical conditions impacting mobility over past year as determined by the PI
- Having known chronic illnesses/disorders that may independently affect study outcome measures: type 1 diabetes mellitus, neurologic (e.g. epilepsy), developmental (developmental delay, autism spectrum disorder), endocrine (thyroid, Cushing's), hepatic, autoimmune, cardiac and renal disorders. Also, chronic lung disorders except well controlled asthma that does not require permanent use of inhaled/oral steroids

Title: Immunometabolism in Pediatric Obesity

PI: [name].

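### The secondary hsCRP analysis defines inflammation by a top-quartile split with no stated reference set or comparator; continuous log(hsCRP) would be better defined and, if the relation is roughly linear, more powerful

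*Combined protocol and SAP*

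**What the plan says.** The hsCRP comparison appears once, at the end of Preliminary Data, in a passage that turns from the limits of the pilot data to the proposed study: "we will compare subjects with hsCRP values in the top quartile to the other groups". Its purpose is "to determine whether the % glycolysis is higher in CD4⁺T cells from those obese subjects with inflammation". Membership of the top quartile is therefore the working definition of inflammation.

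The section on hypotheses and aims makes raised inflammatory markers part of the Aim 1 hypothesis, which contrasts such obese children with lean children, but gives no threshold. Data Analysis contains no hsCRP analysis, categorical or continuous. Its three contrasts and its power statement concern the lean, healthy overweight/obese, insulin-resistant and T2D groups.

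The background text describes CRP by fixed levels. It cites "greater than 80% of very obese adolescents having CRP >1mg/L as compared to 18% of lean adolescents", and from an adult study "a CRP level greater than 3mg/L". The planned split uses neither level.

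Study Population gives the numbers: recruitment is planned "with the goal that approximately 80 subjects stratified across the following groups will complete the study", namely about 20 lean, 40 overweight/obese and 20 overweight/obese with T2D.

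**The concern.** This split is the only stated analysis that brings an inflammation marker to bear on the Aim 1 hypothesis. It has three weaknesses.

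- **The inflamed share is fixed in advance.** A quartile labels one child in four whether few or most have raised CRP, and the cut depends on who enrols. Another study could not reproduce it.
- **The comparison is not fully defined.** The set over which the quartile is taken and the children it is compared with are both left open, and the answer changes what is being estimated.
- **A continuous measurement is reduced to two categories.** If glycolysis rises steadily with hsCRP, this discards information in a study of about 80 children.

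At stake is a diluted, low-powered contrast: a real association between inflammation and T-cell metabolism could be missed, or reported against a threshold that has no meaning outside this sample.

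**Working it through.** **Inputs.** From Study Population: 20 lean children and 60 overweight/obese children (40 + 20), 80 in all. From Data Analysis: 0.05 significance level, taken as two-sided. From the background: 18% of lean adolescents above 1 mg/L. Assumptions: the proportion of overweight/obese children above 1 mg/L (varied below) and the correlation between log(hsCRP) and % glycolysis.

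**1. The plan's own power figure.** Noncentral t with 76 error degrees of freedom and four groups of 20:
- Contrasts (i) and (ii), 40 v 20 at 0.8 SD: noncentrality 0.8/√(1/40 + 1/20) = 2.92, power 0.82.
- Contrast (iii), 20 v 20 at 0.9 SD: noncentrality 0.9/√(1/20 + 1/20) = 2.85, power 0.80.

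The stated value of about 0.80 is reproduced. It does not involve hsCRP. No power is given for the hsCRP comparison.

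**2. Children labelled.** 0.25 × 80 = 20 for a whole-sample quartile; 0.25 × 60 = 15 for a quartile within the overweight/obese.

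**3. Children above 1 mg/L left unlabelled.** Let p be the assumed proportion among the 60. With a whole-sample quartile the number is 20 × 0.18 + 60p − 20; with a quartile within the 60 it is 60p − 15.

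| p | Whole-sample quartile | Quartile within the 60 |
|---|---|---|
| 30% | 1.6 | 3 |
| 40% | 7.6 | 9 |
| 50% | 13.6 | 15 |
| 60% | 19.6 | 21 |
| 80% | 31.6 | 33 |

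The number reaches zero at p = (20 − 3.6)/60 = 27% for the whole-sample quartile and at 15/60 = 25% for the other.

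**4. Information kept by the split.** This step assumes a normal log(hsCRP), a linear relation and all other children as comparator. Relative efficiency of a cut at the 75th percentile:

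φ(0.674)² / (0.25 × 0.75) = 0.3178² / 0.1875 = 0.539

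The loss is 46%: 80 children carry the information of about 43, and 60 that of about 32. With the effect linear on a predictor of another shape, the loss is 36% (gamma, exponential), 39% (mildly lognormal), 44% (uniform) or 56% (strongly lognormal).

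**5. Power.** The split shrinks the correlation by √0.539 = 0.734, so 0.30 becomes 0.220. Fisher-z power is Φ(atanh(r)·√(n − 3) − 1.96):

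| n | Continuous, r = 0.30 | Split, r = 0.220 |
|---|---|---|
| 80 | Φ(2.716 − 1.96) = 0.78 | Φ(1.964 − 1.96) = 0.50 |
| 60 | Φ(2.337 − 1.96) = 0.65 | Φ(1.690 − 1.96) = 0.39 |

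The n = 60 row is the relevant one for an unadjusted analysis confined to overweight/obese children. Simulation (20,000 trials per setting) agrees: 0.78 v 0.51 at n = 80 and 0.65 v 0.39 at n = 60.

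**6. The other reading of the comparator.** If 15 top-quartile overweight/obese children are compared with the 20 lean children, steps 4 and 5 do not apply. A two-sample t-test (33 degrees of freedom) then has power 0.62 at 0.8 SD and 0.72 at 0.9 SD, and the other 45 overweight/obese children do not enter the contrast.

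**The case against.** The strongest reply is that this is one sentence in Preliminary Data about one outcome. The formal contrasts do not use the cut, and CRP is measured as a level, so nothing is lost at collection. That stands, and it limits the point to a secondary analysis.

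Second, if the comparator is the lean group, as the Aim 1 hypothesis would suggest, raised-CRP obese children are not in the reference group and the 46% does not apply. That also stands. The text supports either reading, which is itself a reason to specify it.

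Third, linearity favours the continuous model. If the true relation were a step exactly at the cut, the ranking would reverse: at a split-variable correlation of 0.30 with 80 children, power would be 0.78 split and 0.50 continuous. The documents do not settle the shape.

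A reader might infer that most children with raised CRP will sit in the reference groups. The documents do not support this. The figure above 80% is for very obese adolescents, whereas this study enrols overweight and obese children from age 5. Nor does the protocol define 1 mg/L as its threshold for inflammation.

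A reader might also infer that a null result would be uninformative. That is too strong: under the assumptions of step 4, split power at a correlation of 0.40 with 80 children is about 0.76.

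**Conclusion.** The point holds for a secondary analysis, as an improvement worth making. Two parts need no assumption: the split labels 25% of children whatever their CRP, at a cut that moves with enrolment, and its reference set and comparator are not stated.

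The other parts are conditional. The count of unlabelled children above 1 mg/L runs from about 2 to 33 as the assumed prevalence goes from 30% to 80%. The 46% loss, and the fall in power from 0.78 to 0.50 (n = 80) or from 0.65 to 0.39 (n = 60) at a correlation of 0.30, require a normal log(hsCRP), a linear relation and all other children as comparator. Other predictor shapes give a loss of 36–56%.

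It should not be read as a flaw in the study's main contrasts or their stated power, which reproduce and do not depend on hsCRP.

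**What to change.** Add a short paragraph to Data Analysis:

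- Analyse % glycolysis by regression on continuous log(hsCRP) among the overweight/obese children, and report the slope with its 95% confidence interval.
- Give the unadjusted slope first, and add metabolic group as a sensitivity analysis. Adjustment is debatable because the background treats metabolic dysfunction as a consequence of inflammation.
- Keep the quartile, with its reference set and comparator named, or a cut at 1 or 3 mg/L, as descriptive only.
- Keep the comparison with lean children for the Aim 1 hypothesis. A slope within the overweight/obese answers a different question and does not replace it.

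The cost is one paragraph and one regression; hsCRP is already to be measured. The downside is the assumption of approximate linearity in log(hsCRP), which a plot can check, and lower power than the split if the true relation is a step at the cut.
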